14.3 Vital Signs

14.3.1 Analysis for the Open-label Safety Analysis Set

Vital signs are assessed at Screening, Baseline, and Weeks 2, 4, 8, and 12 during the open-label period.

Respiration rate, systolic blood pressure, diastolic blood pressure, and pulse rate, weight, height (only at Screening), and derived BMI will be summarized using descriptive statistics at Baseline and Weeks 2, 4, 8, and 12 during the open-label period. The change from Baseline values will also be summarized at the Weeks 2, 4, 8 and 12.

Vital sign values will be considered PCI if they meet both the observed value criteria and the change from baseline criteria listed in [Table 7](#). The number and percentage of subjects with PCI vital sign values at Weeks 2, 4, 8, and 12, and overall post-baseline during the open-label period will be summarized for selected parameters. For the overall post-Baseline summaries, all post-Baseline values during the open-label period will be considered, including unscheduled and out of window values. Subjects with multiple PCI values for a given parameter will be counted only once for that parameter. For the by-visit summary, the numerator for the percentage is the number of subjects with a post-baseline PCI vital sign value during the open-label period for the given parameter and visit, and the denominator is the number of subjects with non-missing values for the given parameter and visit. For the overall post-baseline summary, the numerator for the percentage is the number of subjects with at least 1 post-baseline PCI vital sign value during the open-label period for the given parameter, and the denominator is the number of subjects with at least 1 post-baseline vital sign value during the open-label period for the given parameter. Subjects with any post-baseline PCI values will be presented in an additional listing.

14.3.2 Analysis for the Double-blind Safety Analysis Set

In addition to the open-label assessments at Screening, Baseline and Weeks 2, 4, 8, and 12, vital signs are assessed at Weeks 13, 14, 16, 18, 22, 26, 30, 34, and 38 during the double-blind period.

Vital sign summaries for the Double-Blind Safety Analysis Set will be similar to those described above for the Open-Label Safety Analysis Set and will include the following:

- Observed values and change from open-label baseline by visit including both open-label and double-blind visits; overall minimum and maximum for the open-label period; overall minimum and maximum for the double-blind period.
- Observed values and change from double-blind baseline by visit for the double-blind period; overall minimum and maximum for the double-blind period.
- Incidence of PCI values by visit including both open-label and double-blind visits; open-label overall post-baseline; double-blind overall post-baseline.
- Incidence of PCI values by visit for the double-blind period; double-blind overall post-baseline.

Table 7 Criteria for PCI Vital Signs

Vital Sign Parameter	Unit	Criteria ^a		
		Observed Value	And/Or	Change Relative to Baseline
Systolic blood pressure (supine or sitting)	mmHg	≥180	And	Increase of ≥20
		≤90	And	Decrease of ≥20
Diastolic blood pressure (supine or sitting)	mmHg	≥105	And	Increase of ≥15
		≤50	And	Decrease of ≥15
Pulse (supine or sitting)	bpm	≥120	And	Increase of ≥15
		≤50	And	Decrease of ≥15
Weight	kg	Not Applicable		Increase of ≥7%
				Decrease of ≥7%

^aA post-baseline value is considered as a PCI value if it meets both criteria for observed value and change from baseline.

14.4 Electrocardiogram

14.4.1 Analysis for the Open-label Safety Analysis Set

All ECGs will be centrally read; the interpretation by the central cardiologist is considered the official interpretation. 12-lead electrocardiogram (ECG) assessments are performed at Screening, Baseline, Weeks 2 and 12 during the open-label period.

ECG results (ventricular rate, PR, QRS, QT, and QTcF intervals) will be summarized using descriptive statistics at Baseline, Weeks 2 and 12 during the open-label period. The change from Baseline values will also be summarized at the Weeks 2 and 12.

QTcF (msec) observed and change from Baseline values during the open-label period will also be classified into the following categories:

- Observed: ≤450, 451 to 480, 481 to 500, and >500
- Change from Baseline: ≤10, 11 to 30, 31 to 60, and >60

The number and percentage of subjects in each category will be summarized at each visit and for the overall post-baseline maximum during the open-label period.

Electrocardiogram variable values will be considered PCI if they meet or exceed the upper limit values listed in [Table 8](#). The number and percentage of subjects with PCI ECG values at Weeks 2 and 12, and overall post-baseline maximum during the open-label period will be

summarized for selected parameters. For the by-visit summary, the numerator for the percentage is the number of subjects with a post-baseline PCI ECG value during the open-label period for the given parameter and visit, and the denominator is the number of subjects with non-missing values during the open-label period for the given parameter and visit. For the overall post-Baseline summary, the numerator for the percentage is the number of subjects with at least 1 post-baseline PCI ECG value during the open-label period for the given parameter, and the denominator is the number of subjects with at least 1 post-baseline ECG value during the open-label period for the given parameter. Subjects with any post-baseline PCI values will be presented in an additional listing.

Overall ECG interpretation at Baseline, Weeks 2 and 12 and overall post-baseline worst interpretation during the open-label period will be summarized descriptively. Within each summary time frame a subject is counted only once in the category with the worst interpretation (“abnormal, clinically significant” is worse than “abnormal, not clinically significant” is worse than “normal”). For overall post-Baseline worst interpretation, all post-baseline interpretations during the open-label period will be considered, including unscheduled and out-of-window interpretations. For the by-visit summary, the denominator for the percentage is the number of subjects with non-missing interpretations during the open-label period at the given visit. For the overall post-Baseline summary the denominator is the number of subjects with at least one post-baseline interpretation during the open-label period.

Overall ECG interpretation results will also be summarized in shift tables, to determine the number and percentage of subjects with results classified as normal and abnormal at Weeks 2 and 12, and overall post-Baseline worst interpretation during the open-label period. For the by-visit shift summary, the denominator is the total number of subjects with non-missing results at Baseline and the given visit during the open-label period. For the overall post-Baseline summary the denominator is the number of subjects with a non-missing Baseline and at least one post-baseline result during the open-label period.

14.4.2 Analysis for the Double-blind Safety Analysis Set

In addition to the open-label assessments at Screening, Baseline and Weeks 2 and 12, ECG assessments are performed at Weeks 18, 26, and 38 during the double-blind period.

ECG summaries for the Double-Blind Safety Analysis Set will be similar to those described above for the Open-Label Safety Analysis Set and will include the following:

- Observed values and change from open-label baseline by visit including both open-label and double-blind visits.
- Observed values and change from double-blind baseline by visit for the double-blind period.
- Categorical analysis of QTcF Observed Values and Change from open-label Baseline by Visit including both open-label and double-blind visits; overall maximum for the open-label period; overall maximum for the double-blind period.
- Categorical analysis of QTcF Observed Values and Change from double-blind Baseline by Visit for the double-blind period; overall maximum for the double-blind period.
- Incidence of PCI values by visit including both open-label and double-blind visits; open-label overall post-baseline; double-blind overall post-baseline.
- Incidence of PCI values by visit for the double-blind period; double-blind overall post-baseline.
- Overall interpretation by visit including both open-label and double-blind visits; overall worst interpretation for the open-label period; overall worst interpretation for the double-blind period.
- Overall interpretation shift from open-label baseline by visit including both open-label and double-blind visits; overall worst interpretation for the open-label period; overall worst interpretation for the double-blind period.
- Overall interpretation shift from double-blind baseline by visit for the double-blind period; overall worst interpretation for the double-blind period.

Table 8 Criteria for PCI ECG Values

ECG Parameter	Unit	High PCI Criteria
QRS Interval	msec	≥120
PR Interval	msec	≥220
QTcF	msec	>500
QTcF: change from baseline	msec	>60

14.5 Physical and Neurological Examinations

14.5.1 Analysis for the Open-label Safety Analysis Set

Physical examinations and neurological examinations (cranial nerves, motor, sensory, reflexes, gait, and coordination), are performed at Screening, Baseline, and Week 12 during the open-label period.

Physical and neurological examination results (normal, abnormal, and not done) will be summarized in a frequency table by body/neurological system at Baseline and Week 12.

14.5.2 Analysis for the Double-blind Safety Analysis Set

In addition to the open-label assessments at Screening, Baseline and Week 12, physical examinations and neurological examinations (cranial nerves, motor, sensory, reflexes, gait, and coordination), are performed at Weeks 22 and 38 during the double-blind period.

Summaries for the Double-blind Safety Analysis Set will include both the open-label and double-blind periods.

Physical and neurological examination results (normal, abnormal, and not done) during the open-label and double-blind periods will be summarized in a frequency table by body/neurological system.

14.6 Global Clinician Assessment of Suicidality

14.6.1 Analysis for the Open-label Safety Analysis Set

Global Clinician Assessment of Suicidality (GCAS) scores are measured at Screening, Baseline, and Weeks 2, 4, 8, and 12 visits during the open-label period. The number and percentage of subjects for each GCAS rating (0-4) will be tabulated by visit. The number and

percentage of subjects reporting any post-Baseline GCAS score of 3 or 4 during the open-label period will also be tabulated.

14.6.2 Analysis for the Double-blind Safety Analysis Set

In addition to the open-label assessments at Screening, Baseline and Weeks 2, 4, 8, and 12 during the open-label period, CGAS is assessed at Weeks 13, 14, 16, 18, 20, 22, 24, 26, 30, 34, 38 during the double-blind period. Summaries for the Double-blind Safety Analysis Set will include both the open-label and double-blind periods.

The number and percentage of subjects for each GCAS rating (0-4) will be tabulated by visit. The number and percentage of subjects reporting any post-Baseline GCAS score of 3 or 4 during the open-label period and during the double-blind period will also be tabulated .

14.7 Mini-Mental State Examination

14.7.1 Analysis for the Open-label Safety Analysis Set

Mini-Mental State Examination (MMSE) scores are measured at Screening, Baseline, and Weeks 2, 4, 8, and 12 during the open-label period.

Observed MMSE scores will be summarized using descriptive statistics at Baseline, Weeks 2, 4, 8, and 12. The change from Baseline scores at Weeks 2, 4, 8, and 12 values will also be summarized.

14.7.2 Analysis for the Double-blind Safety Analysis Set

In addition to the open-label assessments at Screening, Baseline and Weeks 2, 4, 8, and 12, MMSE scores are measured at Weeks 13, 14, 16, 18, 22, 26, 30, 34, and 38 during the double-blind period. Summaries for the Double-blind Safety Analysis Set will include both the open-label and double-blind study periods.

Observed MMSE values and change from open-label baseline will be summarized by visit for both open-label and double-blind visits.

Observed MMSE values and change from double-blind baseline will be summarized by visit for the double-blind visits. In addition, treatment comparisons will be made between the placebo group and the pimavanserin group (20 mg and 34 mg combined) for change from

double-blind baseline using the MMRM and an ANCOVA model respectively described in [Sections 13.3.1.1](#) and [13.3.1.2](#).

14.8 Extrapyramidal Symptom Rating Scale - Abbreviated

14.8.1 Analysis for the Open-label Safety Analysis Set

Extrapyramidal Symptom Rating Scale - Abbreviated (ESRS-A) scores are measured at Baseline and Week 12 during the open-label period.

Observed ESRS-A total scores and the four individual global CGI-S scores will be summarized using descriptive statistics at Baseline and Week 12. The change from Baseline values will also be summarized at Week 12.

14.8.2 Analysis for the Double-blind Safety Analysis Set

In addition to the open-label assessments at Baseline and Week 12, ESRS-A scores are measured at Weeks 13, 14, 16, 18, 22, 26, 30, 34, and 38 during the double-blind period. Summaries for the Double-blind Safety Analysis Set will include both the open-label and double-blind study periods.

ESRS-A total scores and the four individual global CGI-S scores, along with change from open-label baseline, will be summarized by visit for both open-label and double-blind visits.

ESRS-A total scores and the four individual global CGI-S scores, along with change from double-blind baseline, will be summarized by visit for the double-blind visits.

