6.3.6 Extrapyramidal Symptom Rating Scale

The ESRS ([Chouinard and Margolese 2005](#)) was developed to assess drug induced movement disorders such as Parkinsonism, akathisia, dystonia and tardive dyskinesia with

established reliability, validity and sensitivity. It has demonstrated excellent inter-rater reliability in idiopathic Parkinson's disease ([Chouinard et al. 1984](#)). It consists of a questionnaire of Parkinsonian symptoms, physician examination of Parkinsonism, dyskinetic movements and global impression of tardive dyskinesia. The ESRS-A, an accepted modified form of the original ESRS, will be used during treatment to monitor for any worsening in extrapyramidal symptoms or signs at scheduled visits.

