9.5.9 Additional Subgroup Analyses

Selected analyses will be performed in subgroups defined by dementia subtype:

- AD or FTD-spectrum disorders
- VaD
- PDD or DLB

Subgroup analyses by region will also be provided.

Additional subgroup analyses may be specified in the statistical analysis plan. Subgroup analyses will be performed for both the open-label and double-blind periods.

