5.1 General Data Reporting Conventions

In general, listings will be sorted by randomized treatment group (placebo, pimavanserin), enrolled but not randomized, screen failure (screened but not enrolled), and subject ID, and all relevant data will be presented. Data from screen failures will be included in listings where available.

For continuous variables, the following summary statistics will be provided: number of subjects, mean, standard error of the mean (SE), standard deviation (SD), minimum, maximum, and median. For pharmacokinetic data, the geometric mean will also be provided. Unless specified otherwise, means, medians, and confidence intervals (CIs) will be presented to one more decimal place than the raw data, and the standard deviations and standard errors will be presented to 2 more decimal places than the raw data.

For categorical variables, summaries will include the number and percentage of subjects in each category, using the number of subjects with non-missing values as the denominator for

the percentages (unless otherwise specified). Categories with zero counts will not have zero percentages displayed. Percentages will be presented to 1 decimal place.

Unless specified otherwise, all statistical tests will be 2-sided hypothesis tests and all CIs will be 2-sided 95% CIs. Two-sided P-values will generally be presented to 4 decimal places; values less than 0.0001 will be presented as <0.0001.

When converting number of days to months, it will be calculated as the number of days divided by 365.25 and then multiplied by 12. When converting number of days to years, it will be calculated as the number of days divided by 365.25.

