12.5 Examination of Subgroups

12.5.1 Double-Blind Period

Treatment comparisons will be made with respect to the primary and key secondary efficacy variables using the Cox regression described in Sections 13.1 and 13.2 for the following subgroups:

- Region (North America, Western Europe, Eastern Europe, Asia Pacific, Latin America)
- Designated dementia subtype (Alzheimer's disease or FTD spectrum disorders, Vascular dementia, Parkinson's disease dementia or dementia with Lewy bodies)
- Parkinson's disease dementia (yes)
- Alzheimer's disease (yes)
- FTD spectrum disorders (yes)

- Dementia with Lewy bodies (yes)
- Age group (<75 or ≥75 years old)
- Sex (male or female)
- Primary race (white or non-white)
- Screening dementia severity (mild, moderate, severe)
- OL Baseline antidementia medication (memantine and/or acetylcholinesterase inhibitors) use (yes, no)
- Antipsychotic use within 14 days of screening (yes, no).
- OL Baseline MMSE (<18, ≥18)

For each subgroup, Kaplan-Meier curves of time to relapse and time to discontinuation from the double-blind period for any reason (other than termination of the study by the sponsor) will be presented for each treatment group. The hazard ratios with corresponding 95% CIs obtained from the Cox regression model for each subgroup will be presented in forest plots for the primary and key secondary efficacy variables.

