14 SAFETY ANALYSES

The safety endpoints for this study are as follows:

- Treatment-emergent adverse events (TEAEs)
- Serious adverse events (SAEs)
- Withdrawals due to adverse events (AEs)
- Potentially clinically important changes in other safety assessments
- Global Clinician Assessment of Suicidality (GCAS) score

- Mini-Mental State Examination (MMSE) score
- Extrapyramidal Symptom Rating Scale A (ESRS-A) score

For the open-label period, safety data will be summarized for the Open-label Safety Analysis Set. The following summaries will be provided:

1. all subjects combined;
2. by randomization status (not randomized and randomized);
3. by final dose level (20 and 34 mg) of open-label pimavanserin administered during the open-label period.

For the double-blind period, safety data will be summarized for the Double-blind Safety Analysis Set. The following summaries will be provided:

1. by treatment group (placebo and pimavanserin)
2. by dose level (20 and 34 mg) of pimavanserin administered during the double-blind period for the pimavanserin group.

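### SAP 14.8 summarizes ESRS-A only descriptively by visit, pooled over dementia subtypes, without the subscales and without counting subjects who worsen, so it cannot by itself support a motor-safety statement for the parkinsonian dementias

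*SAP*

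**What the plan says.** Protocol 2.4.1 lists the ESRS-A score as a safety endpoint, and protocol 6.3.6 says the scale is used "to monitor for any worsening in extrapyramidal symptoms or signs at scheduled visits". Protocol 9.5.4 calls for descriptive statistics on its total score and on all of its subscales.

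SAP 14.8.1 covers the open-label period: "Observed ESRS-A total scores and the four individual global CGI-S scores will be summarized using descriptive statistics at Baseline and Week 12". SAP 14.8.2 covers the double-blind period: "ESRS-A total scores and the four individual global CGI-S scores, along with change from double-blind baseline, will be summarized by visit". It adds the same summary for change from open-label baseline. Under SAP 5.1 each continuous summary contains "number of subjects, mean, standard error of the mean (SE), standard deviation (SD), minimum, maximum, and median".

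SAP 14 splits double-blind safety data by treatment group and "by dose level (20 and 34 mg) of pimavanserin administered during the double-blind period for the pimavanserin group". Dementia subtype is not among the splits.

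Protocol 9.5.9 says "Selected analyses will be performed in subgroups defined by dementia subtype", without naming the analyses. The SAP's own list is in 12.5. For the double-blind period, "Treatment comparisons will be made with respect to the primary and key secondary efficacy variables using the Cox regression". For the open-label period, 12.5.2 covers response rates and SAPS scores. Neither section mentions a safety endpoint.

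**The concern.** Parkinson's disease dementia and dementia with Lewy bodies form one of the three subtype strata used for randomization. Appendix B makes a Parkinson's disease diagnosis a core feature of the first. Appendix C lists parkinsonism as a core feature of the second and severe neuroleptic sensitivity as a suggestive feature. Readers will want an answer on motor safety in these subjects, and the protocol itself treats absence of motor worsening as a point in the drug's favour (1.3.1, 1.3.2).

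A table pooled over subtypes answers a different question. It averages these subjects with a majority, or at least a mixture, whose motor baseline may be quite different. It also does not say how many subjects worsened. The omitted subscales include the 10-item Parkinsonism subscale defined in SAP 5.2.13, which is the most direct measure of the sign in question. At stake is whether a sentence such as no motor worsening in dementia-related psychosis would have any table behind it for the parkinsonian subtypes.

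**Working it through.** **1. Subscales.** Protocol 9.5.4 requires the total score and all subscales. SAP 5.2.13 defines four: Parkinsonism (10 items), dyskinesia (6), dystonia (6) and akathisia (2), giving 24 items and a total of 0-120. SAP 14.8 summarizes the total and four single-item 0-5 global ratings. The global ratings are separate items, not the subscale sums. SAP 20 says there are no planned deviations from the protocol's analyses, so the two documents disagree.

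**2. Counts of affected subjects, by safety endpoint.**

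| Endpoint | Subject-level count in the SAP |
|---|---|
| Laboratory (14.2) | shifts, including to overall minimum and maximum; potentially clinically important values |
| Vital signs (14.3) | potentially clinically important values |
| ECG (14.4) | QTcF categories, potentially clinically important values, shift to worst interpretation |
| GCAS (14.6) | any post-baseline 3 or 4 |
| MMSE (14.7) | none, but MMRM and ANCOVA comparisons between arms |
| ESRS-A (14.8) | none, and no comparison between arms |

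**3. Which values reach a by-visit table.** SAP 5.3.4 keeps the assessment closest to the target day in each window. The rule that all post-baseline values count applies only where an extreme value is analysed, and ESRS-A has no such analysis. Example: the Week 26 visit has target double-blind day 99 and window 92-112. A subject seen on day 99 who terminates early on day 110 contributes the day 99 score, and the termination score is left out of the table.

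**4. Dilution.** The documents give no ESRS-A planning figure, no PDD/DLB share and no ESRS-A SD. The one planning input used is 89 subjects per arm. It reproduces: with exponential relapse (60% and 35% over 26 weeks) and 25% dropout, the event probabilities are 0.533 and 0.307, mean 0.420, and 75/0.420 = 178.6 against the stated 178.

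Let f be the stratum's share (equal in both arms), δ a mean difference present only in that stratum, and σ the SD there.
- Pooled difference = f × δ.
- Standardized contrast in the stratum = δ / (σ√(2/(fn))); pooled = fδ / (s√(2/n)), where s is the pooled SD. Their ratio is (s/σ)/√f.
- Equal SDs: s = σ, ratio = 1/√f.
- SD elsewhere half as large: s = σ√(f + (1−f)/4), ignoring the small between-stratum term; ratio = √(f + (1−f)/4)/√f.

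| Assumed f | Stratum per arm (89f) | A 4-point δ appears as | Ratio, equal SDs | Ratio, half SD elsewhere |
|---|---|---|---|---|
| 10% | 8.9 | 0.4 | 3.2 | 1.8 |
| 20% | 17.8 | 0.8 | 2.2 | 1.4 |
| 25% | 22.3 | 1.0 | 2.0 | 1.3 |
| 40% | 35.6 | 1.6 | 1.6 | 1.2 |

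The 4 points are illustrative. At the same shares, about 36 to 142 of the 356 open-label subjects would be in the stratum. That period has no control arm, so the ratios do not apply to it.

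**5. Follow-up by arm.** Relapsed subjects stop study drug (protocol 3.4). With weekly hazards −ln(0.40)/26 = 0.0352 (placebo), −ln(0.65)/26 = 0.0166 (pimavanserin) and −ln(0.75)/26 = 0.0111 (dropout), mean time on treatment is (1 − 0.40×0.75)/0.0463 = 15.1 weeks on placebo and (1 − 0.65×0.75)/0.0276 = 18.5 weeks on pimavanserin. A crude worst-value count would give the drug arm more opportunity to record a worsening.

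**The case against.** The strongest reply is that motor harm is not expected. Protocol 1.2 reports no appreciable dopaminergic activity, 1.3.1 reports no motor worsening in Parkinson's disease psychosis, and 1.3.2 reports no negative effect on UPDRS Part III in the Alzheimer's study. This stands. A reader might infer that extrapyramidal harm is to be expected in the PDD/DLB stratum; the documents do not support that. Neuroleptic sensitivity in Appendix C is a diagnostic feature, not a statement about this drug. Low expected risk does not, however, let a pooled table confirm its absence in a given stratum.

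A reader might also infer that only means are shown and that large individual worsenings vanish. That goes too far. SD, median, minimum and maximum are given, Parkinsonism has its own global rating, individual scores are listed, and adverse events and neurological examinations are tabulated. None of these is planned by subtype, and a maximum does not say how many subjects worsened.

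Nor can subjects outside the stratum be presumed free of motor change. Progressive supranuclear palsy requires an akinetic-rigid syndrome (Appendix E), and corticobasal criteria include rigidity or akinesia (Appendix F). Both sit in the Alzheimer's/frontotemporal stratum, so a split by randomization stratum alone would repeat part of the problem.

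Finally, the SAP splits no safety endpoint by dementia subtype, MMSE also lacks a worsening count, and table specifications are in a separate document not available here (SAP 1). These points lower the weight of the concern. They do not restore the missing subscales or provide a subtype table in the SAP.

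**Conclusion.** The gap holds. SAP 14.8 provides by-visit descriptive statistics pooled over subtypes, no count of subjects who worsen, and no subscales despite protocol 9.5.4. Those tables alone cannot support a motor-safety statement for subjects with parkinsonian dementias.

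The omission of the subscales is a plain discrepancy and needs no assumption. The dilution to f times the effect is exact only if shares are equal by arm and there is no effect elsewhere. Its size cannot be computed from the documents, because the share, the SDs and any effect are unknown. A firm gain of 1.6-3.2 times should not be read into it: that range needs equal SDs, and it falls to 1.2-1.8 if the SD elsewhere is half. No ESRS-A test is planned, so these ratios describe visibility in a table, not a lost decision.

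**What to change.** In SAP 14.8.1 and 14.8.2:

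1. Add the four subscales, including Parkinsonism, to the total score and global ratings. This brings the SAP into line with protocol 9.5.4 and makes the statement in SAP 20 true on this point.
2. Add descriptive summaries of all of these, observed and change from baseline, by designated dementia subtype, and by treatment group within subtype in the double-blind period. Show progressive supranuclear palsy and corticobasal subjects separately from Alzheimer's disease where numbers allow.
3. Add, by treatment group and subtype, the number and percent of subjects whose global rating worsens from baseline to the worst post-baseline value. Use all post-baseline values, including early-termination and unscheduled ones, as SAP 5.3.4 already does for extreme values. Show exposure time alongside, or give an exposure-adjusted rate, because follow-up will differ between arms.

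The cost is SAP wording and a few more tables from data already collected, using a factor already recorded for randomization. Cells will be small, about 9-36 per arm in the PDD/DLB stratum at the assumed shares and 178 randomized, so the tables should be labelled descriptive only. Setting them out before the interim unblinding avoids a post hoc look.
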